Randomization: Individual patients and patient-caregiver dyads will be randomized in a 1:1 fashion to either: 1) Usual care defined as including both a PCP and neurologist; or 2) Usual care augmented by an outpatient interdisciplinary palliative care team. Randomization will be stratified by site, presence of caregiver, presence of dementia using Movement Disorders Society Guidelines for PD-related dementia and the Montreal Cognitive Assessment,^{53, 54} and performed in balanced blocks to minimize potential biases.

Description of the Intervention and Comparator Arms: Comparator: Usual care will consist of care from the patient's primary care physician (PCP) and a neurologist. We consider this the current standard on the basis of evidence showing that care with a neurologist results in better outcomes (e.g. falls, mortality) than care with a PCP alone.⁶ For patients without a neurologist, we will arrange appointments with a neurologist covered by their insurance or a patient assistance program. Patients will be asked to see their neurologist at least every 3 months to match the frequency of visits in the intervention arm and may see their PCP at their typical frequency. Data collection for those in the Usual care arm could occur in person, over the phone, using mailed or electronic survey distribution, or via telemedicine. To ensure treatment fidelity, investigators will not serve as neurologists in the comparator arm.

Intervention Arm: Out intervention will consist of Usual Care plus the addition of an outpatient interdisciplinary palliative care team. Palliative care visits will be performed in person (or telemedicine if needed for rural areas and/or limited transportation) every 3 months and will include consultation with all team members. In addition, visits will be supplemented by optional phone calls one week after each visit to confirm understanding of team recommendations and at 6 weeks to check-in with patient and caregiver. Data collection for those in the Intervention arm could occur in person, over the phone, using mailed or electronic survey distribution, or via telemedicine. Patients and caregivers may also contact the team as needed. Summaries of visits will be sent to the patient, caregiver, PCP and neurologist. The palliative team will enact changes related to core palliative care issues (Table 1) and make suggestions for care outside of palliative care issues to be sent to the patients' Usual Care team.

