
Service Utilization: Health care utilization data will be collected at baseline, and every 6 weeks along with the economic outcome assessments including information on caregiver and patient use of healthcare services (i.e. emergency room services, hospitalizations, hospice and palliative care services, respite care and other stays in long-term care facilities, home health services, and caregivers' use of psychological health services) as well as outpatient visits to physicians or other services. We will also record place of service (e.g. home, community, tertiary center) and number of medications taken. Utilization measures will use items from the AHCR, MEPS and HPQ.

Statistical Analyses: To estimate economic outcomes, all costs will be aggregated for each 6 week period and expressed as a rate per 30 days (monthly costs). Our primary economic comparison will be for total care costs plus non-medical costs in the period preceding the 6-month visit using a mixed regression model with adjustments made for site, baseline costs and work behaviors of the caregiver. Secondary economic models will examine differences by specific source of cost (e.g. missed work, informal caregiving, direct healthcare costs) and will use linear regression analyses to determine whether patient or caregiver variables (e.g. gender, age, cognitive status) are predictive of costs under either interventions. We will also conduct sensitivity analyses of these cost measures (e.g., measuring cost of missed work and informal caregiving time using both a human capital approach and local wages of home health aides for caregivers not employed at baseline).

Our primary service utilization analysis will compare number of hospitalizations, emergency room visits and nursing home placement between groups. T-tests and regression analyses will be used for continuous outcomes, Poisson regression will be used for count outcomes, and chi-square association tests, Fisher's exact association tests, and logistic regression will be used for binary outcomes. Secondary analyses will examine utilization and place of service for ancillary therapies (e.g. physical, occupational and speech therapy). We will use regression models to determine if total number of medications is associated with QOL and ZBI (as it was in our Preliminary data) and whether palliative intervention influences medication use.

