Sample Size and Power Calculations: A two sample T-test with a sample size 125 subjects per group (250 total) could detect an effect equal to 42% of the standard deviation with 90% power and an alpha level of 0.05. For the cost per month model with longitudinal data, if the contrast is the difference in mean total cost between treatment groups after 6 months of follow up, then a sample size of 125 per group (250 total) would achieve

90% power for an effect of 1.75 sd*months (0.29 sd on average) and an alpha level of 0.05. Here sd is in cost per month. If the contrast is the difference in mean total cost between treatment groups after 12 months of follow-up time, then an effect size of 3 sd*months (0.25 sd on average). The power calculations assume a compound symmetric covariance structure with a correlation of 0.5 for repeated measures on a patient.

For a binary outcomes, the following arrangements achieve 90% power with an alpha level of 0.05 and a sample size of 125 per group (250 total): 26% for the control group and 10% for the treatment group, a difference of 0.16 and an odds ratio of 0.316; 50% for the control group and 30% for the treatment group, a difference of 0.2 and an odds ratio of 0.429. For a Poisson count outcome, if the control rate is 0.5 per person year, and the exposure time is one year, then a sample size of 125 per group (250 total) would achieve 90% power with a rate ratio of 0.53 and an alpha level of 0.05.

Aim 3: Identify opportunities to optimize outpatient palliative care by: a) describing PD patient and caregiver characteristics associated with intervention benefits; and b) through direct patient and caregiver interviews.

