Participants: Participants for Aim 3a will be identical to Aim 1. For Aim 3b (qualitative interviews), we will select a subgroup of participants and caregivers using purposive sampling to complete an additional interview following the final study visit to assess patient/caregiver satisfaction and suggestions of optimization of services and delivery. We will initially use a convenience sample, however as the study progresses we will use maximum variance sampling to ensure heterogeneity in terms of study site, gender, age, PD severity, and cognitive status. We may also use contextual information brought up in interviews or through Aim 3A to inform recruitment. We will interview patients assigned to both the intervention and usual care group as patients in the usual care arm may have less biases related to our service model or personal interactions with our team.

Primary Outcomes: Our primary outcome variables will be change at 6 months in the QOL-AD and ZBI. We will also look at symptom burden, mood, grief and spiritual wellbeing in secondary models.

Predictor Variables: Patient features will include: age, gender, medical comorbidities, presence of a caregiver, depression and disease severity (Hoehn and Yahr score). Caregiver features will include age, gender, depression, and socioeconomic status. Other variables including educational attainment, living situation (independent, assisted living, nursing home), location (rural, suburban, urban) and race/ethnicity will also be examined if sufficient variability in data permits.

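### The Aim 2 service-utilization analysis lists unadjusted tests beside regressions and names neither a primary method nor covariates, although baseline use and randomization strata are available

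*Combined protocol and SAP*

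**What the plan says.** The service-utilization part of Aim 2, Statistical Analyses, opens: "Our primary service utilization analysis will compare number of hospitalizations, emergency room visits and nursing home placement between groups". The methods follow: "T-tests and regression analyses will be used for continuous outcomes, Poisson regression will be used for count outcomes, and chi-square association tests", then "Fisher's exact association tests, and logistic regression will be used for binary outcomes". Nothing says which method is primary for which outcome, or what the regressions contain besides treatment.

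Three other places bear on this.

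- Aim 2, Service Utilization: "Health care utilization data will be collected at baseline, and every 6 weeks along with the economic outcome assessments".
- Aim 2, Statistical Analyses, the preceding paragraph on cost: a mixed model with "adjustments made for site, baseline costs and work behaviors of the caregiver".
- Aim 1, Randomization: "Randomization will be stratified by site, presence of caregiver, presence of dementia".

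The Aim 2 power section gives 0.42 SD for a plain T-test with 125 per group. It gives smaller detectable differences for the longitudinal cost contrasts (0.29 and 0.25 SD on average), with this planning assumption: "The power calculations assume a compound symmetric covariance structure with a correlation of 0.5 for repeated measures on a patient".

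On nursing homes, the eligibility criteria do not mention residence. The Aim 3 predictor list includes "living situation (independent, assisted living, nursing home" among variables to be examined only if they vary enough, and gives no time of collection. Placement is not defined.

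**The concern.** T-tests, chi-square tests and Fisher's exact test cannot take a covariate. If they carry the utilization comparisons, the analysis discards baseline use and the stratification factors, both of which the trial will already hold. If the regressions carry them, the covariates are still open, and the choice among tests and covariate sets could be made after the data are seen.

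The plan's prediction that use will move away from emergency visits and hospitalization rests on these comparisons. At stake are precision, most of all for continuous measures, and a fixed analysis. For nursing home placement there is also a question of meaning: without a definition, two analysts could differ on whether a patient who already lives in a nursing home can contribute an event.

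**Working it through.** **Inputs from the documents.** 125 per group after dropout; alpha 0.05 (taken as two-sided; sidedness is not stated); 90% power; correlation 0.5 with compound symmetry; binary scenarios 26% vs 10% and 50% vs 30%; Poisson control rate 0.5 per person-year for one year, rate ratio 0.53; a three-month recall period (Specific Aims, Aim 2).

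**1. The plan's unadjusted figures.**

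- Continuous: detectable difference = (1.960 + 1.282) × sqrt(2/125) = 0.410 SD (0.412 by the exact t calculation). Power at 0.42 SD: 0.42/0.1265 − 1.960 = 1.360, or 91.3% (91.1% by t).
- Binary, pooled null variance: 26% vs 10% gives (0.16 − 1.960 × 0.0486)/0.0475 = 1.362, or 91.3%. 50% vs 30% gives 90.2%.
- Poisson: 62.5 vs 33.1 expected events. With the null variance at the control rate, power is 90.7%. Other two-sided variants give 84.0% to 86.2%.

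The stated 90% is therefore reached without adjustment; for the Poisson case this depends on the variance form.

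**2. The plan already uses the baseline gain elsewhere.** Adjusting for baseline at correlation r multiplies the SD by sqrt(1 − r²). At r = 0.5, 0.410 × sqrt(0.75) = 0.355 SD, which is the 36% in the Aim 1 power section for change at 6 months. The cost figures reproduce in the same way if follow-up is taken as two or four quarterly periods (my reading):

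| Contrast | Variance, baseline-adjusted | Detectable | Without baseline |
|---|---|---|---|
| 6 months, 2 periods | 0.75 − 0.25 = 0.50 | 0.290 SD | 0.355 SD |
| 12 months, 4 periods | 0.625 − 0.25 = 0.375 | 0.251 SD | 0.324 SD |

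**3. Continuous utilization measures with baseline adjustment.**

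| r | Detectable at 90% | Power at 0.42 SD | n per group for 0.42 SD |
|---|---|---|---|
| none | 0.410 SD | 91.3% | 120 |
| 0.3 | 0.391 SD | 93.6% | 109 |
| 0.5 | 0.355 SD | 97.0% | 90 |
| 0.7 | 0.293 SD | 99.6% | 61 |

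**4. Counts.** Assume gamma frailty with variance k, a baseline mean of 0.5 × 0.25 = 0.125 and a follow-up mean of 0.5. The correlation is 0.125 × 0.5 × k divided by sqrt[(0.125 + 0.125²k)(0.5 + 0.25k)]. This is 0.11 at k = 0.5 and 0.32 at k = 2, so the variance cut is about 1% to 10%. Simulated Poisson regression with robust standard errors, rate ratio 0.53, without and with the baseline count:

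| k | Power, unadjusted | Power, adjusted |
|---|---|---|
| 0.5 | 79.9% | 80.2% |
| 1 | 74.6% | 74.3% |
| 2 | 62.3% | 65.8% |

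The starting power is below 90% because of the assumed frailty, not because of missing adjustment.

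**5. Binary outcomes.** Assume 40% of patients have dementia, with control risks of 50% with and 10% without it, so the overall control risk is 0.4 × 0.5 + 0.6 × 0.1 = 26%. With allocation balanced within strata, simulated power is 93.5% for the plain chi-square test and 95.4% for the stratified test. Under no effect the plain test rejects in 2.9% of trials instead of 5%, which is conservative. The arithmetic agrees: the within-stratum variance is 0.4 × 0.25 + 0.6 × 0.09 = 0.154, against 0.26 × 0.74 = 0.1924. The effective critical value is then 1.960/sqrt(0.154/0.1924) = 2.19, for a size of about 2.9%. The gain is about 2 points even with this strong assumed stratum effect.

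**The case against.** The strongest reply is that the section does name regression for continuous outcomes, Poisson regression for counts and logistic regression for binary outcomes. For counts, regression is the only method listed. The Aim 1 analysis section also sends binary and count outcomes to these models with generalized mixed models, and the Specific Aims speak of changes in utilization, which hints at use of the baseline. This stands against a reading that the comparisons are simply unadjusted: silence on covariates is not exclusion. It does not remove the gap, because no text names a covariate for these outcomes or ranks the regressions above the simple tests.

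Second, the three named primary utilization outcomes are counts or binary, so the large continuous gain does not apply to them. This stands. The correlation of 0.5 is also a planning value for repeated measures, not an estimate for utilization.

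Third, utilization is secondary to cost in Aim 2, and the unadjusted tests keep their type I error. This stands, and it limits the weight of the point.

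A reader might also infer that living situation is recorded at baseline, and that patients already in nursing homes will be counted as placements, with a loss of power. The documents do not support this. No text gives the time at which living situation is collected, placement ordinarily means entry, no proportion of residents is given, and 26% vs 10% is a generic illustration rather than a pair of placement rates. What remains is that the term needs a definition.

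**Conclusion.** The point holds as one of efficiency and pre-specification. The plan leaves both the method and the covariates open for the utilization outcomes while holding the data for a better analysis, and it already adjusts in the neighbouring cost model.

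The gain is material for continuous measures if the correlation with baseline is near 0.5: about 0.36 SD detectable instead of 0.41, and 97% instead of 91% power at 0.42 SD. At r = 0.3 it is modest (0.39 SD, 94%). It is small for hospitalizations and emergency visits (variance cut about 1% to 10%, power change about 0 to 4 points) and for nursing home placement (about 2 points from the dementia stratum). Those last figures rest on assumed frailty, stratum risks and dementia prevalence. The simple tests are not invalid, and no loss of power is claimed for nursing home placement.

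**What to change.** - In Aim 2, Statistical Analyses, make the primary analysis of each utilization outcome a regression: linear for continuous measures, count regression for counts, logistic for binary outcomes. Include treatment, the baseline value of that outcome where it varies, and the randomization strata (site, caregiver presence, dementia). Keep the T-test, chi-square and Fisher's exact tests as support.
- State that nursing home placement means new placement among patients not already resident at baseline. Baseline residence is then constant in that model, so only treatment and the strata enter.
- In Aim 2, Sample Size and Power Calculations, give the baseline-adjusted detectable difference for continuous measures, about 0.36 SD at r = 0.5 and 0.39 SD at r = 0.3, beside 0.42 SD.

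The cost is wording; no extra patients or visits are needed. Adjusted odds ratios are conditional on the covariates, and the placement analysis leaves out any patients already resident. Baseline long-term-care stays are among the utilization items and may identify residents. If they do not, and living situation is not taken at baseline, one baseline question is needed.

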The outcomes will be modeled with mixed regression model analysis, with correlation for repeated measures, at baseline and at 3, 6, 9, and 12 months. The empirical covariance estimator may be used to safeguard against model misspecification. The models will control for time, interaction between treatment and time, and potential baseline confounders, including gender, age, depression, and disease severity. The default model will have linear time trajectories for each treatment group, and linear functions for baseline controlling covariates. The linearity assumptions will be checked. Non-linear functions could be approximated with piecewise linear functions or transforms. The main contrasts will be the difference in areas under the fixed effect change from baseline curves for the palliative and treatment control groups, and the mean difference in change between 6 months and baseline between the groups. Secondary tests will be conducted for the mean difference in change from baseline between the groups at the 3, 9, and 12-month time points. The contrasts, controlled for all covariates, will be tested for significance using T-tests and F-tests, with an alpha level of 0.05. The effect estimates, 95% confidence intervals, and p values will be reported. In the process, the interaction between time and treatment will be tested. If the time trajectories are linear, then all tests are stochastically equivalent to the time by treatment interaction test with one parameter. Binary outcomes and count outcomes will be analyzed with logistic regression and Poisson regression respectively. Generalized mixed models will account for repeated measures. We plan to perform subgroup analyses for patients with dementia, severe disease, and depression and may perform exploratory subgroup analyses depending on primary results.

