from models using all available data for a response variable will be compared to the models with missing data methods. The random effects linking together the joint models will be tested. The missing data methods assume missing at random (MAR). Randomization will be checked for baseline variables with summary statistics and two-way tables. Covariates can partially control for deviations from ideal randomization. Homoskedascity and approximate normality for the outcomes will be checked with standard methods. Homoskedascity can be remedied with heterogeneous variance structures or weights. Non-normality should not be much of an issue, unless severe, and can be dealt with using standard methods such as logarithmic transformations. With our sample size the parameter estimates should be consistent and asymptotically normal because of the Central Limit Theorem. All variables will be checked for outliers, and influential outliers will be considered for removal using standard tests (e.g. Cook's D).

Sample Size and Power Considerations: Allowing for up to 25 dropouts per group by the 6-month time point, a two sample T-test with 125 samples per treatment group (250 total) will detect a difference in our continuous outcomes equal to 42% of the standard deviation with 90% power and an alpha level 0.05. This is greater than the suggested minimal clinically significant change for the QOL-AD of 3 points.⁷⁰ For our secondary measure of QOL the difference of half the standard deviation for the PDQ-39 has been suggested in prior studies to be clinically important and detectable with change over time or with outpatient interventions.^{63, 71, 72} For the ZBI, assuming 110 complete dyads per group would diminish our effect size to 44% of the standard deviation with 90% power and an alpha level 0.05. Even a sample of 90 complete dyads would provide an effect size of 0.5 SD/mean. Minimal clinically important differences have not been established for the ZBI but will be estimated in this study using caregiver global impression of improvement and an anchor based approach.⁷³ Notably, prior studies of palliative interventions have found effect sizes of 0.5 SD/mean and greater for the ZBI.¹⁹ The sample size will also enable us to fit models with a large number of parameters and as described below, the longitudinal mixed models and linear time functions will increase our efficiency. Caregivers will be enrolled for each part

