- 1) *As the intervention is enacted by 3 experienced teams at tertiary care centers will it be replicable or relevant for typical clinical practice?* We have taken several measures to ensure that our intervention is replicable across study sites and other centers. Our first planned manuscript will include our study protocol and a detailed description of our intervention and clinic related forms to allow dissemination to interested sites. Our study neurologists have not completed formal palliative training; rather the clinic structure itself is the key to providing the time and interdisciplinary skills needed to address patient and caregiver needs.
- 2) *What if the intervention is not successful in meeting primary or secondary outcomes?* This will be an important, if undesired, result that would still contribute to this field and suggest a need for alternate approaches. The value of Aim 3 will be heightened in this scenario by examining benefits to subgroups (suggesting a need for better screening) and eliciting patient and caregiver input on services and delivery.
- 3) *What if recruitment is slow or retention below expected?* Our recruitment goals are modest and similar goals have been achieved by investigators at all study sites. If needed, further recruitment efforts may include adding additional local sites through community partners and/or more aggressive advertising strategies. A high

drop-out rate would also be an important data point suggesting a need to revise delivery method.

4) *This population is heterogenous and it is possible that outcomes may not apply to all subgroups or that important outcomes for particular subgroups are missed.* This is a significant challenge facing palliative care for PD which may be one factor hampering palliative research for this disease versus more homogenous illnesses such as amyotrophic lateral sclerosis and Alzheimer's disease.⁸² As this heterogeneity is a naturally occurring feature of PD we have made every effort to include the full spectrum of PD in our screening forms and intervention. Aim 3 will provide subgroup analyses to inform future interventions and screening efforts.

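### The Aim 2 utilization counts are assigned Poisson regression with no committed handling of overdispersion or follow-up time, and the 90% power assumes Poisson variance and a full year of exposure for everyone

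*Combined protocol and SAP*

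**What the plan says.** Aim 2, Statistical Analyses, defines the comparison: "Our primary service utilization analysis will compare number of hospitalizations, emergency room visits and nursing home placement between groups". The method given for counts is "Poisson regression will be used for count outcomes". It is listed beside t-tests, chi-square and Fisher's exact tests, which take one value per patient. That section names no offset, dispersion check, robust variance, random effect or negative binomial alternative for the counts, and no time window for them. In the same section, costs are put on a per-30-day rate and their primary comparison gets a mixed regression model.

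Aim 2, Sample Size and Power Calculations, plans the count outcome as Poisson, under the condition "if the control rate is 0.5 per person year, and the exposure time is one year". On that basis it claims power of 90% to detect a rate ratio of 0.53 with 125 patients in each arm, testing at the 0.05 level.

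Two passages under Aim 1 bear on this. Its Statistical Analysis section says "Binary outcomes and count outcomes will be analyzed with logistic regression and Poisson regression respectively", adds that generalized mixed models will account for repeated measures, and makes the empirical covariance estimator optional. Its Sample Size and Power Considerations derive 125 per group from 300 randomized: "Allowing for up to 25 dropouts per group by the 6-month time point".

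**The concern.** Poisson regression sets the variance of each patient's count equal to its mean. That fails when patients with the same covariates have different underlying rates of admission or emergency attendance. The usual standard error is then too small, the interval too narrow, and a chance difference between arms is declared significant more often than 5% of the time.

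There is reason to expect such variation. The sample combines Parkinson's disease with faster-progressing atypical disorders that may make up one-third of it (Significance) and includes patients with and without dementia (Innovation, item 4). Separately, patients who leave early have less time in which to be admitted. If one arm loses more patient-time, a comparison that ignores exposure makes that arm look as if it uses less care.

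Aim 2 predicts a shift away from emergency visits and hospitalizations, and this analysis is the test of that prediction.

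**Working it through.** **Inputs from the documents.** Control rate 0.5 per person-year; exposure one year; 125 per group; rate ratio 0.53, so the treatment rate is 0.5 × 0.53 = 0.265; alpha 0.05, taken as two-sided because the plan does not say; up to 25 of 150 lost per group (16.7%) by 6 months.

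**Assumed.** The negative binomial dispersion k, where variance = mean + k × mean². At the control rate the variance-to-mean ratio is φ = 1 + 0.5k. The documents give no value, so a range is shown.

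**1. The plan's own figure.** The Signorini sample-size formula for Poisson regression reproduces it:

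N = [1.96 × √4 + 1.2816 × √(2 + 2/0.53)]² / [0.5 × (ln 0.53)²] = (3.920 + 3.079)² / (0.5 × 0.4031) = 243, and power at N = 250 is 90.7%.

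A two-sided Wald test of the log rate ratio on the same inputs has SE = √[(1/0.5 + 1/0.265)/125] = √(5.774/125) = 0.2149. Then 0.6349/0.2149 = 2.954 and power = Φ(2.954 − 1.96) = 84.0%. So 90% depends on the formula even with no overdispersion.

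**2. Effect of overdispersion.** With equal follow-up:

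- Two-sided error of a model-based Poisson test: 2 × [1 − Φ(1.96/√φ)].
- Interval width relative to a correct one: 1/√φ.
- Valid (negative binomial Wald) power at 125 per group: Φ(0.6349/√[(5.774 + 2k)/125] − 1.96).
- Number per arm for 90% power: (1.96 + 1.2816)² × (5.774 + 2k)/0.4031.

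| k | φ | Error | Interval width | Power at 0.53 | n per arm for 90% |
|---|---|---|---|---|---|
| 0 | 1.0 | 5.0% | 100% | 84% | 151 |
| 0.5 | 1.25 | 8.0% | 89% | 78% | 177 |
| 1 | 1.5 | 11.0% | 82% | 72% | 203 |
| 2 | 2.0 | 16.6% | 71% | 62% | 255 |

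In simulation (40,000 runs, 150 per arm, k from 0 to 2), Poisson with an offset and robust standard errors brought the error back to about 5–6%.

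These rows use a 12-month mean of 0.5. Over 6 months the mean is 0.25 and φ = 1 + 0.25k, so k = 1 and k = 2 give ratios of 1.25 and 1.5 and errors of 8% and 11%.

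**3. Effect of follow-up alone (k = 0, no offset).** Assume dropouts leave uniformly over the first 6 months, so each contributes 0.25 year on average.

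- Balanced loss of 16.7% per arm: mean exposure is 0.167 × 0.25 + 0.833 = 0.875 year. Simulated error is about 5.4%, with no bias.
- Differential loss, assumed 10% versus 23%: mean exposures are 0.1 × 0.25 + 0.9 = 0.925 and 0.233 × 0.25 + 0.767 = 0.825. The null rate ratio becomes 0.825/0.925 = 0.89 and simulated error is about 10%. With the offset the ratio returns to 1.00 and the error to about 5%.

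The 10% versus 23% split only illustrates the mechanism; the documents give no differential figure.

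**4. Exposure in the power statement.** The 125 per group is the number expected to remain at 6 months. The power statement gives each of them 12 months, and the plan states no allowance for loss after month 6.

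**The case against.** The strongest reply is that the Aim 1 Statistical Analysis already covers these counts. The Aim 1 measures in Table 2 are scales, indices and ratings, none of them an event count, so the sentence on Poisson regression and generalized mixed models may well be meant for the utilization items. These are collected at baseline and every 6 weeks, and the mixed-model provision is firm rather than optional. A patient random effect on 6-weekly counts would absorb patient-to-patient variation, and unobserved periods would contribute nothing, which also deals with follow-up time. This reduces the gap but does not close it. The Aim 2 section sets out its own methods, gives costs a mixed model and counts only Poisson regression, and does not refer back. An analyst following it could fit plain Poisson to patient totals.

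Other parts of the reply stand in full:

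- A reader might infer that raw counts will be compared without regard to time. The text is silent on an offset and does not exclude one, and the power section works in rates per person-year.
- A reader might infer that the false-positive rate is known to be well above 5%. That depends on a dispersion the documents do not give. The remark "This population is heterogenous and it is possible that outcomes may not apply to all subgroups" (Potential Problems and Alternative Strategies, item 4) concerns subgroups, not the spread of counts.
- A reader might take the refusals described under Significance as evidence that usual care will lose more patients. They concern agreeing to enrol and be randomized, and the only dropout allowance is equal by arm. If usual care did lose more, its count would fall and the bias would work against the intervention.
- Part of the fall from 90% power is due to the formula.
- The trial's primary outcomes are the QOL-AD and the ZBI. Specific Aims makes cost the primary outcome of Aim 2 and places utilization under secondary analyses.

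**Conclusion.** The point holds as a gap in specification, with a conditional consequence. The Aim 2 count analysis does not commit to handling overdispersion or follow-up time, and its power rests on Poisson variance and a full year for all 125 per group.

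If plain Poisson is fitted and the variance-to-mean ratio is 1.25 to 2, two-sided error is about 8% to 17% and valid Wald power is about 78% to 62%. The fair baseline for that power is 84%, not 90%. With no overdispersion the error is 5%. Some overdispersion is likely in this population, but its size is an assumption throughout.

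Unequal follow-up is a lesser matter. Balanced loss at the planned level leaves the error near 5.4%. Omitting an offset biases the rate ratio only if follow-up differs by arm, and the documents do not support any particular difference. The stronger conclusion, that intervals will certainly be too narrow and the error rate well above 5%, does not follow from the plan.

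**What to change.** In Aim 2, Statistical Analyses:

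- Make one of these the rule for hospitalizations and emergency visits, not an option: negative binomial regression, Poisson regression with the empirical (robust) variance, or Poisson with a patient random effect on the 6-weekly counts. If the Aim 1 mixed-model provision is meant to apply, say so there.
- Include log observed follow-up time as an offset and state the time window for the comparison.
- Optionally adjust for baseline utilization, which is already collected.

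In Aim 2, Sample Size and Power Calculations, name the power formula and show power over a range of dispersion, such as the table above.

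This is a change of wording and needs no new data, visits or patients. The downside is somewhat wider intervals and a less favourable power statement for an Aim 2 outcome.
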